7.13.2. Analyses of Laboratory Data

Laboratory measurements (chemistry, hematology, and urinalysis) will be analyzed using continuous data (change from baseline) and categorical data (proportion of treatment-emergent

abnormalities). If there are multiple records of laboratory measurements at baseline or post-baseline visit, the last record will be used.

Summaries and analyses for continuous data will be performed separately using conventional units (CN units) and also International System of Units (SI units). Summaries and analyses for categorical data will be performed using the International System of Units (SI units). The list of laboratory parameters analyzed is provided in [Appendix 3](#).

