7.13.2.2. Analyses of Categorical Data

7.13.2.2.1. Treatment-Emergent High, Low, or Abnormal Analyses

Treatment differences in the proportion of participants with treatment-emergent high or treatment-emergent low, or treatment-emergent abnormal laboratory values at (1) anytime and (2) each postbaseline visit will be assessed using Fisher's exact test.

Treatment-emergent high laboratory measurements are values which are low or normal at the baseline visit and fall into the high category at post-baseline visit(s). Similarly, treatment-emergent low laboratory measurements are values which are high or normal at the baseline visit and fall into the low category at post-baseline visit(s). Treatment-emergent abnormal laboratory measurements are values which are normal at baseline and fall into the high category or low category at postbaseline visit(s).

[Table A4.SAP.3](#) describes which participants will be included in the denominator and numerator when assessing treatment-emergent abnormalities.

Table A4.SAP.3. Denominator and Numerator for Treatment-Emergent Laboratory Analyses

Treatment-Emergence Category	Denominator	Numerator
Treatment-Emergent High	Participants who are normal or low at baseline	Participants who are high postbaseline (among participants who were low or normal at baseline)
Treatment-Emergent Low	Participants who are normal or high at baseline	Participants who are low postbaseline (among participants who were high or normal at baseline)
Treatment-Emergent Abnormal	Participants who are normal at baseline	Participants who are low or high postbaseline (among participants who were normal at baseline)

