7.13.2.2.2. Shift Tables and Additional Analyses

For urinalysis categorical parameters, baseline normal to post-baseline abnormal shifts will be summarized at any time. Fisher's exact test will be used to compare shifts in urinalysis parameters between treatment groups.

The proportion of participants with treatment-emergent changes from a low value or normal value at all baseline at any time in the following analytes will be summarized by treatment group. Changes of interest are:

- ALT: The number and percentage of participants with a measurement greater than or equal to 1 time (1X), 3 times (3X), 5 times (5X), 10 times (10X), and 20 times (20X) the performing lab upper limit of normal (ULN)
- AST: The number and percentage of participants with a measurement greater than or equal to 1 time (1X), 3 times (3X), 5 times (5X), 10 times (10X), and 20 times (20X) the performing lab ULN
- ALP: The number and percentage of participants with a measurement greater than or equal to 2 times (2X), and 3 times (3X) the performing lab ULN
- TBL: The number and percentage of participants with a measurement greater than or equal to 2 times (2X), 5 times (5X), and 8 times (8X) the performing lab ULN
- DBL: The number and percentage of participants with a measurement greater than or equal to 2 times (2X) and 5 times (5X) the performing lab ULN
- GGT: The number and percentage of participants with a measurement greater than or equal to 2 times (2X) the performing lab ULN

Comparisons between treatment groups will be carried out using Fisher's exact test.

Additionally, plots of TBL versus ALT values and TBL versus AST values will be produced.

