7.13.3. Analyses of Vital Signs and Weight

Vital sign measurements (including weight) will be analyzed using continuous data (change from baseline) and categorical data (proportion of treatment-emergent abnormalities).

If there are multiple records of vital sign or weight measurements at baseline or post-baseline visit(s), the last record will be used.

The analyses will be done for the following vital sign measurements and weight:

- systolic blood pressure
- diastolic blood pressure
- pulse
- temperature, and

- weight.

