7.13.3.2. Analyses of Categorical Data

Treatment differences in the proportion of participants with treatment-emergent high, treatment-emergent low or treatment-emergent abnormal vital sign measurement will be assessed between treatment groups using Fisher's exact test at (1) anytime (2) each post-baseline visit.

Treatment-emergent high vital sign measurements are the values which are low or normal at the baseline visit and fall into the high category at post-baseline visit(s). Similarly, treatment-emergent low vital sign measurements are the values which are high or normal at the baseline visit and fall into the low category at post-baseline visit(s). Treatment-emergent abnormal vital sign measurements are the values which are normal at the baseline visit and fall into the high or low category at post-baseline visit(s). The criteria for post-baseline low and post-baseline high are provided in [Table A4.SAP.4](#).

For each vital sign at each postbaseline visit, only participants who had a baseline result and had a non-missing result at that postbaseline visit will be included in the denominator when computing the proportion of participants with treatment-emergent high, low, or abnormal values.

Summary and analyses of change from baseline in weight will be provided. The proportion of participants with a weight gain or loss of greater than or equal to 4 percent of baseline body weight will be compared between treatment groups using Fisher's exact test at each visit and at any time. In addition, categories of BMI (underweight = < 18.5 , normal = $\geq 18.5 - < 25$, overweight = ≥ 25 to < 30 , obese = ≥ 30) will be compared between treatment groups using Fisher's exact test at (1) anytime and (2) each post-baseline visit.

Table A4.SAP.4. Criteria for Abnormal Vital Signs and Weight

Vital Sign Parameter (Unit)	Postbaseline Low Criteria	Postbaseline High Criteria
Systolic Blood Pressure (mmHg)	Absolute value ≤ 90 and ≥ 20 decrease from baseline	Absolute value ≥ 160 and ≥ 20 increase from baseline
Diastolic Blood Pressure (mmHg)	Absolute value ≤ 50 and ≥ 10 decrease from baseline	Absolute value ≥ 100 and ≥ 10 increase from baseline
Pulse (bpm)	Absolute value < 50 and ≥ 15 decrease from baseline	Absolute value > 100 and ≥ 15 increase from baseline
Weight	$\geq 4\%$ decrease	$\geq 4\%$ increase
Vital Sign Parameter	Postbaseline Criteria for Abnormality	

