7.13.4. Analyses of Electrocardiograms

Electrocardiogram (ECG) measurements will be analyzed using continuous data (change from baseline) and categorical data (proportion of treatment-emergent abnormalities).

Since ECG is measured in triplicates, the average of triplicates will be used for baseline and postbaseline visit(s). If there are multiple records after averaging ECG triplicates within a visit, the last record of averages will be used.

The analyses will be done for the following ECG measurements:

- heart rate
- PR interval
- QRS duration
- QT interval, and
- QTc interval.

All analyses of QTc will be carried out using the Fridericia correction (QTcF) method. These summaries will include data from each visit at which ECG measures are performed.

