7.13.4.2. Analyses of Categorical Data

Incidence of treatment-emergent abnormal ECGs will be compared between treatment groups by Fisher's exact test at (1) anytime and (2) each post-baseline visit.

Abnormal ECG criteria are presented in [Table A4.SAP.5](#) and criteria for abnormal QTcF prolongation are presented in [Table A4.SAP.6](#).

Table A4.SAP.5. Criteria for Abnormal ECG Parameters

ECG Parameter	Low Criteria	High Criteria
Heart Rate	≤ 40 bpm	≥ 120 bpm
PR Interval	≤ 120 msec	≥ 220 msec
QT Interval		> 500 msec
QRS Duration	< 60 msec	≥ 120 msec

Abbreviations: bpm = beats per minute; ECG = electrocardiogram; msec = millisecond.

Table A4.SAP.6. Criteria for Identifying Participants with a Prolonged ECG QTcF Interval

Criterion Number	Criterion
1	In adult males, QTcF > 450 msec; in adult females, QTcF > 470 msec
2	QTcF ≥ 500 msec
3	Increase of > 0 msec and ≤ 30 msec relative to baseline
4	Increase of > 30 msec and ≤ 60 msec relative to baseline
5	Increase of > 60 msec relative to baseline
6	Increase of > 60 msec relative to baseline and QTcF ≥ 500 msec

Abbreviations: ECG = electrocardiogram; msec = millisecond; QTcF = Fridericia's corrected QT interval.

Treatment-emergent high ECG parameters (heart rate, PR interval, QRS duration, QT and QTcF intervals) are the values which are low or normal at the baseline visit and fall into the high abnormal categories at post-baseline visit(s) in [Table A4.SAP.5](#) and [Table A4.SAP.6](#) postbaseline. Similarly, treatment-emergent low ECG parameters (heart rate, PR interval, QRS duration) are the values which are high or normal at the baseline visit and fall into the low abnormal categories at postbaseline visit(s) above.

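### The last-record rule for laboratory, vital-sign and ECG data has no exception for any-time counts, so a threshold crossing followed by a normal repeat at the same visit is not counted

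*SAP*

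**What the plan says.** Three parent sections of the SAP choose one record when a visit has several.

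- **Laboratory (7.13.2):** "If there are multiple records of laboratory measurements at baseline or post-baseline visit, the last record will be used".
- **Vital signs and weight (7.13.3):** "If there are multiple records of vital sign or weight measurements at baseline or post-baseline visit(s), the last record will be used".
- **ECG (7.13.4):** triplicates are averaged first, and then "If there are multiple records after averaging ECG triplicates within a visit, the last record of averages will be used".

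Each parent section also announces that the data will be analysed both as change from baseline and as treatment-emergent abnormalities. The categorical subsections then ask for counts over the whole period:

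- 7.13.2.2.1 compares participants with "treatment-emergent abnormal laboratory values at (1) anytime and (2) each postbaseline visit".
- 7.13.2.2.2 covers multiples of the upper limit of normal (ULN) for ALT, AST, ALP, total and direct bilirubin, and GGT: "The proportion of participants with treatment-emergent changes from a low value or normal value at all baseline at any time".
- 7.13.3.2 compares abnormal vital signs "at (1) anytime (2) each post-baseline visit".
- 7.13.4.2 compares abnormal ECGs, including the QTcF criteria, "at (1) anytime and (2) each post-baseline visit".

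None of these subsections says that all records, or the most extreme record, feed the any-time count.

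**The concern.** An any-time count answers whether a participant ever crossed a threshold during treatment. Choosing the last record at each visit answers a narrower question: whether the participant was over the threshold on the final record of some visit. The two differ whenever an abnormal value is followed by a normal repeat under the same visit.

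Repeats need not be unrelated to the result. Protocol 10.2.12 and Attachment 2 call for monitoring and consultation on follow-up tests once ALT or AST exceeds 3X ULN or total bilirubin exceeds 2X ULN, and 3X and 2X are also cut-points in SAP 7.13.2.2.2. Attachment 2 lets the investigator order tests when clinically indicated, and Protocol 10.2.3 allows extra ECGs. An abnormal value is more likely than a normal one to prompt a repeat, so the net effect of the rule should be under-counting.

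At stake are the outlier tables for liver tests, blood pressure, pulse and QTcF. The efficacy analyses are not touched.

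**Working it through.** The documents give no figure for this rule, so there is nothing to reproduce. The check has three steps.

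**1. Is there an exception?** The selection rules in SAP 7.13.2, 7.13.3 and 7.13.4 were read against 7.13.2.2.1, 7.13.2.2.2, 7.13.3.2 and 7.13.4.2. No exception is written. That the rule reaches the any-time counts is therefore an inference from its position in the parent section; the SAP does not say so outright.

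**2. What does the rule do to one participant?** Take an invented participant with normal baseline ALT and these values in multiples of ULN:

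| Visit | Records in order | Last record |
|---|---|---|
| 9 | 0.8 | 0.8 |
| 12 | 3.6, then repeat 0.9 | 0.9 |
| 18 | 0.9 | 0.9 |

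- Last-record rule: maximum = max(0.8, 0.9, 0.9) = 0.9, below 3, so not counted at 3X ULN at any time.
- All records: maximum = 3.6, at or above 3, so counted.

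The rule also works in the other direction: a normal value followed by an abnormal repeat is counted.

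**3. What could it do to a comparison?** This is an illustration only. The arm size (about 575 per arm) is from SAP 6.1. The any-time incidences (2% placebo, 5% solanezumab) and the share f of affected participants lost are assumptions. The same f is applied to both arms.

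- Observed incidence: q = p × (1 − f). Expected count: 575 × q.
- Power (normal approximation, two-sided 0.05) = Φ[(d − 1.96 × se0) / se1], where d = q1 − q0, q̄ = (q0 + q1)/2, se0 = √[2q̄(1 − q̄)/575] and se1 = √{[q0(1 − q0) + q1(1 − q1)]/575}.
- For f = 0: d = 0.03, se0 = √(2 × 0.035 × 0.965/575) = 0.01084, se1 = √[(0.0196 + 0.0475)/575] = 0.01080. Power = Φ[(0.03 − 0.02124)/0.01080] = Φ(0.81) = 0.79.

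| f (assumed) | Expected counts, placebo / solanezumab | Ratio | Difference (percentage points) | Power |
|---|---|---|---|---|
| 0 | 11.5 / 28.8 | 2.5 | 3.00 | 0.79 |
| 10% | 10.4 / 25.9 | 2.5 | 2.70 | 0.75 |
| 25% | 8.6 / 21.6 | 2.5 | 2.25 | 0.67 |
| 50% | 5.8 / 14.4 | 2.5 | 1.50 | 0.49 |

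Equal loss in both arms leaves the ratio unchanged but shrinks the counts, the difference and the power. The SAP's Fisher's exact test would have somewhat lower power throughout. Nothing in the documents indicates which value of f applies.

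**The case against.** **Same-visit repeats may be rare.** Attachment 2 has chemistry, hematology and urinalysis assayed centrally, so an abnormal ALT would not normally be known before the participant leaves. A follow-up test under Protocol 10.2.12 is then a later draw. Protocol 10.2.7 describes redraws only for unusable samples or failed collection, and in those cases the last record is the right one. Protocol 10.2.8 sets no trigger for repeat vital signs, and 10.2.3 ties extra ECG replicates at a time point to record quality. This stands as a limit on size. It does not remove the gap, because nothing says how a repeat is assigned to a visit.

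**The text can be read more generously.** SAP 7.13.2.2.2 counts participants having a measurement above each multiple, and Table A4.SAP.3 counts anyone high after baseline. Either could mean any record. SAP 7.1 bars off-schedule observations only from MMRM, and 7.2 keeps early discontinuers' off-schedule safety data for other analyses, so a repeat filed under a different visit does not overwrite the first value. That leaves two readings, and only the last-record one is written as a selection rule.

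**There is another route.** Protocol 10.2.1.1 requires clinically significant laboratory, ECG and vital-sign findings to be reported, and these can reach the adverse-event tables. That is a real safeguard, but it depends on investigator judgement and does not replace an objective threshold count.

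**Two stronger readings are tempting.** A reader might infer that most liver or QTcF peaks vanish, since extreme values tend to fall on repeat. The documents give no within-person variability, frequency of same-visit repeats or filing convention, so no share can be stated. A reader might also infer that risk at 1600 mg is understated. The rule applies to both arms and every dose, and the SAP's by-dose summaries (7.13.1.3, 7.13.5.1, 7.13.7.1.1) cover adverse events, MRI and suicidality, not these tables.

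**Conclusion.** The gap holds on the text, and it is minor. As written, the last-record rule governs the any-time categorical and threshold analyses, so a crossing followed by a valid normal repeat under the same visit is dropped from those tables. The consequence is possible under-counting in both arms and a weaker safety comparison.

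This rests on three conditions: that the parent-section rule applies to the subsections beneath it, that some repeats are filed under the same visit as the value that prompted them, and that abnormal values prompt repeats more often than normal ones do. The documents support the first by layout. The second and third are plausible but not quantified. The number of participants affected is unknown and may be small. The illustrative power figures show only the direction of the effect and how it would grow with the lost share.

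**What to change.** Add one sentence to each of SAP 7.13.2, 7.13.3 and 7.13.4:

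- Keep last-record selection for baseline and for by-visit summaries and analyses.
- For any-time categorical and threshold analyses, use all valid post-baseline records, whether scheduled, repeat or unscheduled. Take the highest value for high criteria and the lowest for low criteria.
- For ECG, treat each averaged set as one record, so that averaging of triplicates is retained.
- Exclude samples or tracings documented as non-viable or technically invalid, so that a record replaced for quality reasons is not revived.

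This also settles how unscheduled records enter the any-time counts, which the SAP does not state in general. No new data are needed. The cost is that a few more isolated, unconfirmed values will be counted, by the same rule in both arms.

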7.13.2.1. Analyses of Continuous Data

Change from baseline to each postbaseline visit at which laboratory samples are collected will be assessed using an ANCOVA model with treatment as independent factors and baseline value and age as covariate in the model. This analysis will be done separately for each laboratory analyte.

7.13.2.2. Analyses of Categorical Data

7.13.2.2.1. Treatment-Emergent High, Low, or Abnormal Analyses

Treatment differences in the proportion of participants with treatment-emergent high or treatment-emergent low, or treatment-emergent abnormal laboratory values at (1) anytime and (2) each postbaseline visit will be assessed using Fisher's exact test.

Treatment-emergent high laboratory measurements are values which are low or normal at the baseline visit and fall into the high category at post-baseline visit(s). Similarly, treatment-emergent low laboratory measurements are values which are high or normal at the baseline visit and fall into the low category at post-baseline visit(s). Treatment-emergent abnormal laboratory measurements are values which are normal at baseline and fall into the high category or low category at postbaseline visit(s).

[Table A4.SAP.3](#) describes which participants will be included in the denominator and numerator when assessing treatment-emergent abnormalities.

Table A4.SAP.3. Denominator and Numerator for Treatment-Emergent Laboratory Analyses

Treatment-Emergence Category	Denominator	Numerator
Treatment-Emergent High	Participants who are normal or low at baseline	Participants who are high postbaseline (among participants who were low or normal at baseline)
Treatment-Emergent Low	Participants who are normal or high at baseline	Participants who are low postbaseline (among participants who were high or normal at baseline)
Treatment-Emergent Abnormal	Participants who are normal at baseline	Participants who are low or high postbaseline (among participants who were normal at baseline)

7.13.2.2.2. Shift Tables and Additional Analyses

For urinalysis categorical parameters, baseline normal to post-baseline abnormal shifts will be summarized at any time. Fisher's exact test will be used to compare shifts in urinalysis parameters between treatment groups.

The proportion of participants with treatment-emergent changes from a low value or normal value at all baseline at any time in the following analytes will be summarized by treatment group. Changes of interest are:

- ALT: The number and percentage of participants with a measurement greater than or equal to 1 time (1X), 3 times (3X), 5 times (5X), 10 times (10X), and 20 times (20X) the performing lab upper limit of normal (ULN)
- AST: The number and percentage of participants with a measurement greater than or equal to 1 time (1X), 3 times (3X), 5 times (5X), 10 times (10X), and 20 times (20X) the performing lab ULN
- ALP: The number and percentage of participants with a measurement greater than or equal to 2 times (2X), and 3 times (3X) the performing lab ULN
- TBL: The number and percentage of participants with a measurement greater than or equal to 2 times (2X), 5 times (5X), and 8 times (8X) the performing lab ULN
- DBL: The number and percentage of participants with a measurement greater than or equal to 2 times (2X) and 5 times (5X) the performing lab ULN
- GGT: The number and percentage of participants with a measurement greater than or equal to 2 times (2X) the performing lab ULN

Comparisons between treatment groups will be carried out using Fisher's exact test.

Additionally, plots of TBL versus ALT values and TBL versus AST values will be produced.

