- [13] Has ECG obtained during screening that, in the opinion of the investigator, is clinically significant with regard to the subject's participation in the study. Bazett's corrected QT (QTcB) interval must be evaluated and must not exceed >458 msec in males or >474 msec in females.
- [14] At screen, has alanine aminotransferase (ALT/SGPT) values >2X the upper limit of normal (ULN) of the performing laboratory, aspartate aminotransferase (AST/SGOT) values >3X ULN, or total bilirubin values >2X ULN.
- [15] Has a screening MRI scan (Visit 4) with results showing >4 hemosiderin deposits (definite microhemorrhages or areas of superficial siderosis); or any ARIA-E.
- [16] Has any contraindications for MRI studies, including claustrophobia, the presence of metal (ferromagnetic) implants, or a cardiac pacemaker that is not compatible with MRI.
- [17] Resides in a skilled nursing facility.
- [18] Is receiving any medication that has significant central nervous system (CNS) effects that in the investigator's opinion would interfere with cognitive testing and protocol compliance. The procedures manual provides a list of medications that impair cognition that are permitted in the study but need to be withheld prior to cognitive testing.
- [19] Has previously completed or withdrawn from this study or other solanezumab studies, or previous participation in any study investigating active immunization against A β .
- [20] Has previously completed or withdrawn from a study of passive immunization with another antibody within the last 120 days.
- [21] Pregnant, lactating or of child bearing potential (that is, women must be 2 years post-menopausal or surgically sterile to be considered not child bearing potential).
- [22] Is investigator site personnel directly affiliated with this study and/or immediate family, or has a study partner who is investigator site personnel directly affiliated with this study. Immediate family is defined as a spouse, parent, child, or sibling, whether biological or legally adopted.
- [23] Is an ADCS, ATRI, or Lilly employee, or has a study partner who is an ADCS, ATRI, or Lilly employee.

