- Prolonged acute infusion reaction (that is, not rapidly responsive to medication such as antihistamines, nonsteroidal anti-inflammatory drugs, and/or narcotics and/or brief interruption of infusion).

Note: Acute infusion reactions may occur with any agent that causes cytokine release (for example, some monoclonal antibodies or other biological agents). Cytokine release may or may not be related to the mechanism of the infused biologic agent. Signs and symptoms usually develop during or shortly after drug infusion and generally resolve completely within 24 hours.

Signs/symptoms may include: allergic reaction/hypersensitivity (including drug fever), arthralgia, bronchospasm, cough, dizziness, dyspnea, fatigue, headache, hypertension, hypotension, myalgia, nausea, pruritus, rash, rigors/chills, sweating (diaphoresis), tachycardia, urticaria, and vomiting.

- Discontinuation of the study drug for abnormal liver tests should be considered by the investigator when a subject meet 1 of the following conditions after consultation with the medical monitor:
 - ALT or AST >8X ULN
 - ALT or AST >5X ULN for more than 2 weeks

- ALT or AST >3X ULN and total bilirubin level >2X ULN or prothrombin time >1.5X ULN
- ALT or AST >3X ULN with the appearance of fatigue, nausea, vomiting, right upper-quadrant pain or tenderness, fever, rash, and/or eosinophilia (>5%)

In addition, subjects may be discontinued from the study drug and from the study in the following circumstances, including but not limited to:

- Mean QTcB >500 msec and an absolute change >60 msec when compared with baseline (the most recent measurement made at either screening [Visit 1 through 5] or baseline [Visit 6]).
- Enrollment in any other clinical trial involving an investigational product or enrollment in any other type of medical research judged not to be scientifically or medically compatible with this study
- Investigator Decision
 - The investigator decides that the subject should be discontinued from the study.
 - If the subject, for any reason, requires treatment with another therapeutic agent that has been demonstrated to be effective for treatment of the study indication, discontinuation from the study occurs prior to introduction of the new agent.
- Subject Decision
 - The subject requests to be withdrawn from the study.
- Sponsor Decision
 - ATRI or Lilly or its designee stops the study.
- Adverse Event

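### The liver-threshold table in SAP 7.13.2.2.2 leaves out anyone above ULN at baseline for the analyte, so rare hepatic elevations are under-counted; add an all-baseline count

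*SAP*

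**What the plan says.** SAP 7.13.2.2.2 introduces its hepatic summary as the proportion of participants with "treatment-emergent changes from a low value or normal value at all baseline at any time in the following analytes". The threshold rows follow that sentence: ALT and AST at or above 1X, 3X, 5X, 10X and 20X ULN; total bilirubin at 2X, 5X and 8X; and rows for ALP, direct bilirubin and GGT. Arms are compared by Fisher's exact test. Plots of total bilirubin against ALT and AST are added, with no stated baseline restriction.

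The other categorical laboratory analysis has the same restriction. In Table A4.SAP.3 the numerator for treatment-emergent high is "Participants who are high postbaseline (among participants who were low or normal at baseline"), and the denominator is limited in the same way.

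On entry, Protocol 8.2 criterion 14 excludes a candidate only if "At screen, has alanine aminotransferase (ALT/SGPT) values >2X the upper limit of normal (ULN) of the performing laboratory", or "aspartate aminotransferase (AST/SGOT) values >3X ULN, or total bilirubin values >2X ULN". It sets no limit for ALP, GGT or direct bilirubin.

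During treatment, Protocol 8.4.1 asks the investigator to consider stopping study drug under several liver conditions, including "ALT or AST >8X ULN" and "ALT or AST >3X ULN and total bilirubin level >2X ULN or prothrombin time >1.5X ULN". None depends on the baseline value.

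**The concern.** The restriction suits the 1X row, where a participant already above ULN has nothing to cross. It is harder to justify at 3X and above. A screening ALT within the entry limit cannot already be at 3X, so reaching 3X is a new finding whether baseline was 0.8X or 1.5X.

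As written, a participant who enters at ALT 1.2X and reaches 12X ULN meets the protocol's 8X condition but contributes to no ALT row. No other SAP table counts participants by ULN multiple, so the only counted and tested summary of marked enzyme elevation omits eligible participants. In addition, the joint ALT/AST and bilirubin criterion is plotted but never counted.

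**Working it through.** **Who is left out.** The plan states no figure here, so there is nothing to reproduce.

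| Analyte | Screening values above ULN that may enrol | Threshold rows in the table | Can an eligible screening value already meet a row above 1X? |
|---|---|---|---|
| ALT | above 1X, up to 2X | 1X, 3X, 5X, 10X, 20X | No |
| AST | above 1X, up to 3X | 1X, 3X, 5X, 10X, 20X | Only at exactly 3X |
| Total bilirubin | above 1X, up to 2X | 2X, 5X, 8X | Only at exactly 2X |
| ALP, GGT, direct bilirubin | no entry limit | 2X; also 3X (ALP), 5X (direct bilirubin) | Yes |

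The entry limits apply at screening. SAP 7.1 defines baseline as the last non-missing value before the first infusion, and Attachment 1 of the protocol schedules chemistry at Visit 1 and Visit 6. The SAP's words *at all baseline* could mean that one value or every pre-dose value. The second reading would leave out more people. On the natural reading the restriction works analyte by analyte: raised AST with normal ALT still counts in the ALT rows.

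**Fold rise from an eligible raised baseline** (threshold divided by baseline multiple). From ALT 2X: 3/2 = 1.5 to reach 3X, 5/2 = 2.5 to reach 5X, 8/2 = 4 to reach 8X. From AST 3X: 5/3 = 1.67 to reach 5X and 8/3 = 2.67 to reach 8X. None of these is counted for that analyte.

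**How many participants.** Let q be the share above ULN at baseline for an analyte. The documents do not give q; 3%, 5% and 10% are assumptions. With N = 1150: 0.03 × 1150 = 34.5, 0.05 × 1150 = 57.5 and 0.10 × 1150 = 115.

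**Effect on the rate.** Assume 10 true cases among 575 per arm: 10/575 = 1.74%. Under the convention of Table A4.SAP.3 the omitted people leave the denominator too. If k of the 10 cases are lost, the reported rate divided by the true rate is (1 − k/10)/(1 − q).

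| q | k = 1 | Understated by | k = 2 | Understated by |
|---|---|---|---|---|
| 3% | 0.9/0.97 = 0.928 | 7.2% | 0.8/0.97 = 0.825 | 17.5% |
| 5% | 0.9/0.95 = 0.947 | 5.3% | 0.8/0.95 = 0.842 | 15.8% |
| 10% | 0.9/0.90 = 1.000 | 0% | 0.8/0.90 = 0.889 | 11.1% |

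The top of the range needs a strong link between raised baseline and later elevation. At q = 3%, 575 × 0.03 = 17.25 people would supply 2 cases and 557.75 would supply 8, a risk ratio of (2/17.25)/(8/557.75) = 8.1.

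**Effect on the count.** If raised-baseline participants have R times the risk of the others, the share of crossings missed is qR/(1 − q + qR). At R = 1 this equals q. At an assumed R = 3 it is 0.09/1.06 = 8.5%, 0.15/1.10 = 13.6% and 0.30/1.20 = 25% for q = 3%, 5% and 10%.

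**The case against.** A reader might infer that these participants escape every rate and every test. The documents do not support that. Protocol 10.2.1.1 requires clinically significant laboratory findings to be reported. SAP 7.13.1.1 counts events that first occur or worsen after the first infusion, and compares adverse events, serious events and discontinuations due to adverse events by Fisher's exact test. The ANCOVA in SAP 7.13.2.1 has no normal-baseline restriction. This objection stands in part. The adverse event route depends on the investigator's judgement, SAP 7.13.1.4 defines no hepatic cluster, and a mean-change model is poorly suited to a few extreme values.

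A reader might also infer bias between arms. None follows: omission depends on a pre-treatment value in a 1:1 randomised trial, and Protocol 11.2.13.3 itself calls for treatment-emergent proportions.

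Nor does the restriction alone prevent reconciliation with Protocol 8.4.1. The table has no 8X, duration or joint row for anyone, and those conditions are applied case by case after consulting the medical monitor.

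Finally, losing 1 or 2 of 10 cases might be read as a 10-20% understatement of the rate. That holds only if the omitted people stay in the denominator, which Table A4.SAP.3 does not do. The introduction to the protocol names no hepatic signal for solanezumab and reports few laboratory differences in earlier Phase 3 studies, which limits the priority of this point.

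**Conclusion.** The point holds as a gap in safety reporting. Eligible participants above ULN at baseline are missing from the ULN-multiple rows for that analyte and from treatment-emergent high, so rare marked elevations are under-counted. The rate is understated by about 0-17.5% if there are 10 cases per arm, 3-10% of participants have raised baselines, and one or two cases are lost. All three inputs are assumptions, and the upper end implies a much higher risk in the raised-baseline group. The documents show neither bias between arms nor total absence of these participants from the safety analyses. The primary result is unaffected.

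**What to change.** In SAP 7.13.2.2.2:

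- Keep the normal-baseline table, including the 1X row, and replace *at all baseline* with the baseline definition in SAP 7.1.
- Add counts, compared by Fisher's exact test, for ALT and AST at 3X ULN and above and total bilirubin at 2X ULN and above. Include all safety-population participants with a post-baseline value, split by baseline status (at or below ULN, above ULN).
- For ALP, GGT and direct bilirubin, which have no entry limit, show any all-baseline count only by baseline category, or require the value to exceed baseline.
- Add a count of participants with ALT or AST above 3X together with total bilirubin above 2X ULN. Describe it as the bilirubin limb only of the Protocol 8.4.1 condition: Attachment 2 makes coagulation tests optional, local and for lumbar puncture participants, so the prothrombin-time limb cannot be tabulated trial-wide.

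The cost is SAP wording and a few added rows from data already collected; no clinical threshold changes. The downside is that a few participants already near a threshold at baseline will be counted, which the baseline split makes visible.
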